## Study Protocol

### Background

The goal of this campaign is to reduce unnecessary emergency department (ED) visits/encourage patients with low acuity visits to follow up with an appropriate provider and/or to seek care outside of the ED in the future. In this campaign, patients will be assigned to receive or not receive outreach following ED discharge that is aligned with the goal. Outreach will occur via a text message, as well as information added to the patient's after visit summary (AVS), and will include one or more calls to action that make patients aware of other Geisinger resources and avenues through which they can seek care outside of the ED. These may include, but are not limited to, walk-in urgent care, virtual urgent care, primary care provider (PCP) appointments, and/or other ways in which to contact Geisinger. The study will assess whether ED use differs across patients in different outreach conditions. It will also examine whether patients followed through on the message-specific calls to action in the messages differently across conditions.

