### **Other Pre-specified Outcomes**

We will run the analysis described above on the following additional outcomes:

1. PCP appointment scheduled

PCP appointment scheduled (yes/no)

[Time Frame: within 60 days following day of discharge]

2. PCP visit

PCP appointment attended (yes/no)

[Time Frame: within 60 days following day of discharge]

3. Telehealth appointment scheduled

Telehealth appointment scheduled (yes/no)

[Time Frame: within 60 days following day of discharge]

4. Telehealth appointment attended

Telehealth appointment attended (yes/no)

[Time Frame: within 60 days following day of discharge]

5. Urgent care visit

Urgent care appointment attended (yes/no)

[Time Frame: within 60 days following day of discharge]

6. Call made to PCP

Record of patient call to PCP (yes/no)

[Time Frame: within 60 days following day of discharge]

7. Any of the suggested actions taken

PCP called or visited, urgent care visited, telehealth appointment attended, or PCP or telehealth appointment scheduled (yes/no)

[Time Frame: within 60 days following day of discharge]

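### Outcomes 2 and 4, and 7 through them, count appointments booked before the ED discharge; this dilutes them as measures of follow-through and adds variance that the arm-only model leaves in

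*Combined protocol and SAP*

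**What the plan says.** The Background section gives the purpose of the secondary measures: "It will also examine whether patients followed through on the message-specific calls to action in the messages differently across conditions". The SAP section Other Pre-specified Outcomes then defines them.

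- Outcome 2: "PCP appointment attended (yes/no".
- Outcome 4: "Telehealth appointment attended (yes/no".
- Outcome 7, titled as any suggested action being taken: "PCP called or visited, urgent care visited, telehealth appointment attended, or PCP or telehealth appointment scheduled (yes/no".
- Outcomes 1 and 3: "PCP appointment scheduled (yes/no" and "Telehealth appointment scheduled (yes/no".

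All carry the same window: "Time Frame: within 60 days following day of discharge". All reuse the primary model from Planned Analyses, an OLS regression whose only stated predictor is study arm. No section restricts, or adjusts for, appointments that already existed at discharge.

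**The concern.** A patient may leave the ED with a chronic-care or annual visit already booked for three weeks later. If that visit is kept, outcomes 2 and 7 are both yes, although the outreach did not prompt the booking. Two things follow.

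- **Interpretation.** Neither arm's yes-rate can be read as the proportion who acted on the messages. If the outreach works by prompting new bookings, the arm difference shrinks by the pre-booked share.
- **Precision.** Whether a visit was already booked at discharge is a baseline fact that strongly predicts these outcomes. The arm-only model leaves that predictable variation in the residual.

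These outcomes are the trial's evidence on whether patients turned to other care. A weak result on attendance could be taken as a weak response to the outreach when part of the cause is the outcome definition.

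**Working it through.** **1. The plan's own figure.** Inputs from Power Analysis: 5,524 patients, 41% vs 38%, two-tailed alpha .15. The allocation ratio is not stated; 1:1 is assumed, so n = 2,762 per arm. Power = Φ(difference/SE − 1.440), with unpooled SE.

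SE = √[(0.41×0.59 + 0.38×0.62)/2,762] = 0.01315, and 0.03/0.01315 = 2.282. Power = Φ(0.842) = 80.0%, which matches the plan. The figure concerns ED visits only; none is given for outcomes 1–7.

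**2. What each definition counts.** In outcomes 2 and 4 the 60-day window dates attendance, so a visit booked before discharge qualifies. It passes into outcome 7 as a visited or attended component. In outcomes 1 and 3 the window most naturally dates the act of scheduling, which leaves earlier bookings out. The text does not exclude the other reading, an appointment dated within the window.

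**3. Size under assumptions.** None of these rates is in the documents:

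- b = share with a pre-booked visit in the window, all attended;
- r = 0.30, control rate of new attended bookings among the rest;
- d = 0.03, effect on that rate, with no effect in the pre-booked.

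Control rate c = b + (1−b)r; treatment rate t = b + (1−b)(r+d); difference = (1−b)d.

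Summed variance, arm only: c(1−c) + t(1−t).

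Summed variance, adjusted for the pre-booked flag: (1−b)[r(1−r) + (r+d)(1−r−d)] = (1−b)(0.2100 + 0.2211), because the pre-booked are all yes and contribute no residual variance.

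Example, b = 20%: c = 0.440, t = 0.464, difference 0.024.

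- Arm only: SE = √(0.4951/2,762) = 0.01339; 0.024/0.01339 = 1.793; power 64%.
- Adjusted: SE = √(0.3449/2,762) = 0.01117; 0.024/0.01117 = 2.148; power 76%.

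| Pre-booked | Control / treatment | Difference (points) | SE, arm only | Power, arm only | SE, adjusted | Power, adjusted |
|---|---|---|---|---|---|---|
| 10% | 37.0 / 39.7% | 2.7 | 0.01308 | 73% | 0.01185 | 80% |
| 20% | 44.0 / 46.4% | 2.4 | 0.01339 | 64% | 0.01117 | 76% |
| 30% | 51.0 / 53.1% | 2.1 | 0.01344 | 55% | 0.01045 | 72% |
| 40% | 58.0 / 59.8% | 1.8 | 0.01324 | 47% | 0.00968 | 66% |

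Adjustment reduces the SE. It does not undo the shrinkage of the difference.

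**4. Sensitivity.** With b = 20% and r = 10/20/30/40/50/60%, power goes from 70/66/64/64/65/69% to 95/84/76/72/71/73%. Over r = 10–60% and b = 10–40%, adjustment always helps; the smallest gain is about 2 points (r = 60%, b = 10%: 75% to 77%).

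If only 80% of pre-booked visits are kept (b = 20%, r = 30%), then c = 0.16 + 0.24 = 0.400 and t = 0.424. The adjusted variance is 2×0.2×0.8×0.2 + 0.8×0.4311 = 0.4089, and power goes from 65% to 70%. The gain is smaller but still present.

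**5. Counting only new bookings instead.** At r = 30%, if pre-booked patients book anew as often as the others, the comparison is 30% vs 33% and power is 83%. If they never book anew, it is (1−b)×30% vs (1−b)×33%, and power is 78/73/67/61% at b = 10/20/30/40%, below the adjusted analysis throughout. At r = 60%, b = 20%, it gives 64%, against 69% for the plan as written and 73% with adjustment.

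**The case against.** The case for leaving the plan alone has several sound parts.

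- **No bias.** Background asks about differences between conditions. Pre-booked visits are balanced in expectation, so the arm difference estimates the effect on any attendance without bias. This stands. A reader might infer that outcomes 2, 4 and 7 do not measure follow-through at all; the documents do not support that. They measure it in diluted form.
- **Kept visits may serve the aim.** The campaign's goal includes to "encourage patients with low acuity visits to follow up with an appropriate provider". Outreach that helps a patient keep an existing visit could count as success. This stands, and it is a reason not to replace the stated definition.
- **New bookings are already measured.** A reader might extend the concern to outcomes 1 and 3. On their plain reading these date the scheduling after discharge, so they need only a confirming sentence. They also give context for a null result on outcomes 2 or 4.
- **Redefinition is not clearly better.** A reader might conclude that only new bookings should count. Step 5 shows that the result depends on how pre-booked patients behave, which the documents do not tell us.
- **Low stakes.** Only the ED-visit analysis is labelled confirmatory. This stands and limits the weight of the point.

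None of this answers the precision argument: a strong baseline predictor is left out of the model, and including it costs little.

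**Conclusion.** The point holds in a limited form. As defined, outcomes 2 and 4, and 7 through them, include visits booked before discharge. The comparison remains valid for any attendance, but it is diluted as a measure of follow-through and less precise than it could be.

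At an assumed 30% new-booking rate and 3-point effect, adjustment adds roughly 6 to 20 points of power as the pre-booked share rises from 10% to 40%. That range assumes every pre-booked visit is attended and unaffected by the outreach; no-shows reduce the gain. The calculation is generic to an attendance outcome. Outcome 7 also has call and urgent-care components, which were not modelled.

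A reader might infer that these outcomes were mostly settled before the first message. The documents cannot show that. Under the step 3 assumptions, pre-booked visits make up b/c = 27/45/59/69% of control yes results at 10/20/30/40% pre-booked, a majority only at the two higher shares.

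This is a cheap improvement to secondary analyses, not a flaw in the trial's main test.

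**What to change.** 1. Keep outcomes 2, 4 and 7 as stated. Add to their OLS model a baseline yes/no covariate: a PCP or telehealth appointment already booked at the time of the index discharge and dated within the next 60 days. Fix the flag at discharge, whatever later happens to the appointment.
2. As a supportive analysis, report by arm the attended PCP and telehealth appointments whose booking date is after discharge. State how a rescheduled pre-booked visit is classified.
3. Add one sentence confirming that outcomes 1 and 3 date the act of booking, not the date of the appointment.

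The cost is a few lines of SAP text, one extra record extraction and one covariate. Outcomes 1 and 3 on their plain reading already need booking dates. No extra patients or procedures are required. Project Status says no data had been analysed when the document was uploaded; if that is still so, the rule can be set before any results are seen.

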## **Analysis Notes**

Recent work suggests that OLS regressions are appropriate in randomized experiments with binary outcome variables such as ours (Gomila, 2021).

